2. INTRODUCTION

CVD is the most common cause of death among patients with RA. Several studies showed a 50-60% increased risk of death from myocardial infarction and stroke in patients with RA compared with the general population, with the standardized mortality ratio attributable to CVD ranging from 1.13-5.15.¹⁻⁶ Aggressive treatment of RA decreases CVD morbidity and mortality, but there is evidence that many patients do not benefit from the “treat to target” paradigm and do not in fact receive sufficiently aggressive RA treatment. Thus, CVD risk assessment through cholesterol testing among patients with RA remains an important CVD risk reduction strategy.⁷⁻¹¹

Several studies have reported that the prevalence of hyperlipidemia in patients with RA is lower than in those without RA. However, the relationship between lipids, RA, and CVD risk is complicated by RA therapies that have been associated with increased lipid levels.^{12,13} We have reported previously that three different combination therapies were associated with increased lipid levels after 6 months of treatment.¹² Nevertheless, the American Heart Association/American College of Cardiology recommend following their guidelines applicable to the general population for CVD risk assessment, including cholesterol testing.

Although primary care physicians (PCPs) test RA patients’ lipids more frequently than rheumatologists, overall testing remains suboptimal, with only 44% or fewer patients with RA tested, compared with 79% of patients with diabetes mellitus (DM), another CVD risk factor that is more widely appreciated by PCPs. A significant knowledge gap has been reported among PCPs regarding RA as a CVD risk factor, with 68% of PCPs frequently failing to identify RA as a CVD risk factor,¹⁴ suggesting that specific interventions for these patients may be warranted.

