5. STUDY POPULATION

5.1 Study population

Inclusion Criteria

- Have RA
- Age between 40 and 75 years (inclusive)

- Provide a date of their next appointment with their rheumatologist or other physician on their care team
- Willing to work with a peer coach
- Speaks English
- Have a phone
- Has access to the internet
- Resides or lives in the US

Exclusion criteria

- Do not have RA
- Younger than age 40 or older than age 75
- Taking a statin
- Known history of diabetes.
- Known history of CVD defined by:
 - Open heart surgery
 - Coronary angioplasty
 - History of heart failure
 - History of heart attack or stroke

Participants will be screened using a REDCap screening survey. If participants answer yes to any of the exclusion criteria questions, the survey skips to the end, and participants will be informed that they are not eligible. The age range for the inclusion criteria reflects the age range of the current AHA guidelines for risk assessment for CVD. The exclusion of established CVD reflects differences in national guidelines on the management of patients with established CVD vs. preventing CVD. The overall goal of this research is to discover effective strategies to prevent CVD, therefore we focus here on primary prevention.

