Individuals who are interested in participating will respond to the research assistant's contact information on the invitations for ArthritisPower, the survey that Bendcare is administering, and BuildClinical flyers and corresponding survey. An unblinded research assistant from WCM will respond to direct emails from interested individuals to schedule a screening telephone call. The WCM research assistant will also call patients that have indicated on the Bendcare survey, the Twitter REDCap survey, or patients of [name], [name], [name], [name], [name], and [name] who have not marked in EPIC their wish not to be contacted for research. Before the research assistant calls the participants, they will text them from a secure number through Doximity to let them know that they will be calling them shortly. During this phone call, the study will be explained in full. Prior to any study activities, subjects will be screened for eligibility and if eligible, they will review with the unblinded WCM research assistant the Informed Consent form approved by WCM Institutional Review Board (IRB) and which complies with regulatory requirements. Subjects will be given adequate

[figure not shown]
time to consider any information concerning the study given to them by the Investigator or designee. As part of the Informed Consent process, subjects will be given the opportunity to ask the Investigator any questions regarding potential risks and benefits of participation in the study. This informed consent process will be voice recorded during the screening telephone call in the secure HIPAA protected server of WCM Division of General Internal Medicine.

Enrollment and Randomization

We will randomize subjects by a computer-generated random allocation list. The unblinded research assistant will call the subject to complete the enrollment and randomization in the study. The call will consist of the following activities:

- The subject will need to provide the date of their next appointment with their rheumatologist or other physician on their care team .
- The intervention will begin at least 6 weeks before their next appointment and the first data collection point will be at that time.
- Once a subject is enrolled and randomized, the unblinded research assistant will inform the subject the arm they have been assigned to (CARE RA vs self-administered online learning) by phone.

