8. ANALYSIS AND STATISTICS

8.1 Power Calculations and Sample Size

The primary outcome measure is the percentage of patients in each arm that had a lipid panel checked or initiated LLT. Assuming 80% of the subjects in the intervention group have their lipids checked within the 3 months of the study, and 60% of the subjects in the control group have their lipid checked N=64 subjects per group would have at least 80% power to detect a margin difference of 20%, for a one-sided test and significance level of 0.05. We recognize that the sample of 128 subjects is modest, which reflects the pilot nature of the study in the context of a training grant. We will use data from this pilot study to design a more definitive trial powered to detect smaller differences in the primary outcome, and to compare usual care with the intervention.

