8.2 Data Analysis

To analyze the data, descriptive analyses (means, medians, standard deviations, proportions, and frequency distributions) and correlation analyses (Spearman/Pearson rank correlations) will be conducted to assess and describe the cohort. Baseline comparability between study arms will be assessed with parametric and nonparametric analyses including two sample t-tests, Wilcoxon Rank Sum, and Chi-Square tests of proportions. Every effort will be made to keep subjects in the study for the entire follow-up. Analysis will be based on intention-to-treat, regardless of whether the subject completed the intervention program. The primary outcome is the percentage of patients with lipids checked (available now through national laboratory chain) or that reported having their lipids checked. Secondary outcomes include the percentage of subjects that reported initiating LLT, self-efficacy, and patient activation as described above. We will determine these outcomes in each group (self-administered online learning program and the CARE RA arm) as well as differences in these outcomes between the groups. Two-sided t-tests will be used to calculate differences and P values ≤ 0.05 will be considered statistically significant. We will examine differences in socio-demographics, disease severity, and depressive symptoms. These characteristics will be included in a multivariable logistic regression model to determine their association with the outcome (lipids being checked) and potentially increase the statistical power of the test of group differences.

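### Index physician type, which the plan's own background links to lipid testing, is not a listed baseline item or a model covariate, leaving a small, cheaply avoidable loss of precision

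*Combined protocol and SAP*

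**What the plan says.** Section 2 (Introduction) states that primary care physicians test RA patients' "lipids more frequently than rheumatologists, overall testing remains suboptimal". It gives no testing rate by physician type.

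Section 5.1 requires each subject to "Provide a date of their next appointment with their rheumatologist or other physician on their care team". The date is the stated requirement; the kind of physician is not asked for. Section 1 ties the primary objective to that upcoming appointment.

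On allocation, Section 5.4 says "We will randomize subjects by a computer-generated random allocation list" and names no stratification factor. Neither Table 2 (Section 5.5) nor the baseline call (Section 7.3) lists the index physician's type.

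Section 8.2 says "We will examine differences in socio-demographics, disease severity, and depressive symptoms". These characteristics then enter a multivariable logistic model for lipids checked, with added power for the group comparison as one stated purpose. The test actually named for group differences is a different one: "Two-sided t-tests will be used to calculate differences and P values ≤ 0.05 will be considered statistically significant".

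**The concern.** Covariate adjustment gains precision only when the covariate predicts the outcome. The documents tie none of the listed covariates to lipid testing. They do tie the type of physician to it, and that factor is missing. It could be known before allocation, since every subject must already name an appointment to be eligible.

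At stake is some precision in a trial of 128 subjects. There is also a question of timing. Sessions 3 and 4 (Table 3) deal with which doctor should check cholesterol. Both arms are given the online modules, but only the coached arm works through a plan with a coach. If physician type were asked after allocation, the answer could depend on arm and would no longer be a safe covariate.

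**Working it through.** **The plan's own figure.** Section 8.1 gives the inputs: "Assuming 80% of the subjects in the intervention group have their lipids checked within the 3 months of the study", 60% in the control group, "N=64 subjects per group would have at least 80% power to detect a margin difference of 20" percentage points, "for a one-sided test and significance level of 0.05". With the pooled-variance formula (mean rate 0.70):

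n = [1.645·√(2·0.7·0.3) + 0.842·√(0.8·0.2 + 0.6·0.4)]² / 0.2² = (1.066 + 0.532)² / 0.04 ≈ 63.9, so 64 per arm.

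Power at 64 per arm is 80.1% one-sided. The stated figure reproduces. With the two-sided test of Section 8.2, power is 69.9%.

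**Assumptions, not in the documents.** Let f be the share of index visits with a physician other than a rheumatologist, and g the gap in testing rate between the two kinds of visit. I took f from 20% to 50% and g from 10 to 40 points, held the overall rates at 80% and 60%, and kept the effect at 20 points in each group. At f = 30% a 30-point gap is impossible, because the coached rate would be 0.80 + 0.7·0.3 = 1.01. Shares of 20% to 30% are therefore limited to gaps of 20 points.

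**Standard error.** √[(0.8·0.2 + 0.6·0.4)/64] = √(0.40/64) = 0.079, or 7.9 points.

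**Chance imbalance.** The difference between arms in physician mix has SD √[2f(1−f)/64]. At f = 0.5 this is 8.8 points. Multiplied by g, it moves the estimated difference by 1.8 points (1 SD) at g = 20 and by 2.7 points at g = 30; 1.96 SD at g = 30 is 5.2 points. This movement is a component of the 7.9-point SE: √(7.9² − 2.65²) ≈ 7.4.

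**Removable share of the variance.** 2f(1−f)g²/0.40. At f = 0.5, g = 0.3: 2·0.25·0.09/0.40 = 11%.

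**Power.** Simulation with 60,000 trials per case, 64 per arm and simple randomisation, comparing an unadjusted pooled z-test with a Cochran-Mantel-Haenszel (CMH) test by physician type:

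| f | g (points) | Variance removable | One-sided power | Two-sided power |
|---|---|---|---|---|
| 30% | 10 | 1% | 80.5% → 80.3% | 70.6% → 70.2% |
| 30% | 20 | 4% | 80.7% → 81.6% | 70.9% → 71.8% |
| 50% | 20 | 5% | 80.6% → 82.1% | 70.7% → 72.1% |
| 50% | 30 | 11% | 80.8% → 84.4% | 70.9% → 75.4% |
| 50% | 40 | 20% | 80.8% → 88.0% | 70.7% → 79.9% |

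The last row is an extreme: it needs a coached rate of 100% in one group.

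**Stratified allocation.** Added to the CMH test it gives 82.2% (f = 50%, g = 20) and 84.5% (f = 50%, g = 30) one-sided, against 82.1% and 84.4% without it. Stratifying without adjusting gives only 81.4% and 82.0%. Nearly all the gain comes from adjustment.

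**Validity of the unadjusted test.** Under simple randomisation the mean estimate was 0.1995 to 0.2001 against a true 0.20. Type I error was 4.8% to 5.0% one-sided and 5.3% to 5.5% two-sided. In this model each arm's count is binomial at the overall rate whatever the gap, so the gap does not change the size of the test.

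The logistic model itself was not simulated; the CMH test stands in for it.

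**The case against.** The strongest case against the point has five parts.

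- **No bias.** A reader might infer that the omission biases the comparison, or that a swing of about ±5 points is a threat on top of the usual error. Neither follows. Randomisation keeps the estimate unbiased, and the swing is already inside the 7.9-point SE. This part of the objection stands in full.
- **The size is assumed.** The documents give neither the gap nor the visit mix. Recruitment runs through arthritis networks and rheumatology care (Sections 5.3 and 5.4), so a 50% share is not an obvious central case. This stands, and is why the result is given as a range.
- **The outcome is not tied to the index physician.** Section 8.2 counts any lipid check, by laboratory record or self-report. Section 3.1 also counts learning of a test in the past year. A subject with a rheumatology visit may be tested in primary care. This stands: how often each kind of physician tests is not the same as how well the next visit predicts testing, and the simulation does not model that dilution.
- **Adjustment is already planned.** True, but with covariates that the documents do not link to testing, and in a model separate from the named two-sided test.
- **Power is short for another reason.** The fall from 80.1% to 69.9% comes from the one-sided sample size and two-sided analysis. That is a separate matter and lends this point no weight.

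**Conclusion.** The point holds as a small efficiency gain. A factor that the plan itself links to lipid testing is not a listed baseline item and is not adjusted for, so some avoidable variance stays in the primary comparison. The loss is about 0 to 2 points of power for gaps up to 20 points, and about 4 to 5 points for a 30-point gap with half the visits outside rheumatology. Gains of 7 to 9 points appear only in the extreme case. All of these rest on an assumed gap and mix, with an equal effect in both groups, and dilution could bring them lower.

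A reader might also infer that the allocation list has to be stratified. The figures do not support that, since stratification adds less than 1 point of power once the analysis adjusts. The point is worth acting on because it costs almost nothing and cannot be cleanly repaired after allocation.

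**What to change.** 1. At the enrolment call in Section 5.4, where the appointment date is already taken, record before allocation whether that appointment is with a rheumatologist or another physician. Add the item to Table 2 and Section 7.3.
2. Name it as a covariate in the Section 8.2 logistic model, and state that this model's arm term tests the arm difference in lipids checked. A CMH test by physician type would serve equally well. If the covariate sits only in a secondary model beside an unadjusted test, the primary comparison gains nothing.
3. Keep the rest of the covariate list short and named in advance. At the planning rates only 64·0.2 + 64·0.4 = 38.4, about 38 subjects, are expected to be untested.
4. Treat stratified allocation as optional.

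The cost is one enrolment question and one model term, with no added subjects. The pilot would also yield testing rates by physician type for the larger trial that Section 8.1 foresees.

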9. PROGRAM EVALUATION

We will use the RE-AIM Framework for the evaluation of the program. The investigators of CARE RA will use these set of questions within Table 4 to evaluate the CARE RA program with the participants of the program and to guide the approach that investigators will follow to evaluate the reach, effectiveness, adoption, implementation, and maintenance of the program. This will help in the expansion of the program for a larger clinical trial.

Table 4: RE-AIM Evaluation Dimensions for the Cardiovascular Risk Reduction Program for Patients with Rheumatoid Arthritis.

Dimension*	Level
REACH	Individual Level
	
 -What percentage of potentially eligible subjects decided not to participate? -What percentage of potentially eligible subjects were excluded? -What percentage of potentially eligible subjects were enrolled in the program? -How representative of the target population were the subjects that were enrolled? -What proportion of subjects agreed to participate out of the total number of those that were invited and met criteria? -What factors contributed to the participation/non-participation of the subjects? -What might have been done to get more of the target population to participate? 
REACH will be assessed using our REDCap enrollment data, surveys, and focus groups or interviews. Through REDCap, we will be able to determine how many subjects were contacted through ArthritisPower, screened, and enrolled, compared to the overall number of subjects that completed the program. Surveys, focus groups, and interviews will allow us to determine factors that contributed to the use of the program. Through the surveys, focus groups, and interviews, we will conduct a qualitative analysis with subjects in the program so that we can obtain feedback on the reason's subjects chose to participate initially in the program, barriers they faced in enrolling in the program, and reasons why they chose to join or not to join the program.

EFFECTIVENESS	Individual Level
	
 -How many subjects in the CARE RA arm received a cholesterol test during the program compared to the control arm? -How many subjects in the CARE RA arm received a cholesterol test by 1-week post intervention follow up compared to the control arm? -How many subjects in the CARE RA arm received a cholesterol test by 3-months post intervention follow up compared to the control arm? -How many subjects in the CARE RA arm initiated a statin, if indicated, after completion of the program in each arm? - See statistical analysis section for details. -How many subjects saw an improvement in their secondary outcomes (RAPID3, SSS, PHQ-8, PAM, MUSE, and GSE) from baseline to 1-week and 3-month post intervention data collection between arms? -Were you able to understand the program information? -Do you believe the program information is valuable to living a healthy life?
ADOPTION	Organization Level
	
 -What factors contributed to ArthritisPower and its members, and the Bendcare network, to taking up the intervention? -What barriers interacted with the intervention to prevent adoption within ArthritisPower and the Bendcare patient network? 
ADOPTION will be assessed upon completion of the trial through talking with members of the ArthritisPower community and the Bendcare patient network.

IMPLEMENTATION **Individual Level**

- To what extent were the intervention components delivered as intended in the protocol?
- How was the intervention implemented? By whom and when?
- How was the program adapted or modified over time?
- What was it like to deliver this program to individuals with rheumatoid arthritis?
- What do you think was most successful? What were the major barriers in implementing this program?
- What was it like to conduct the weekly sessions?
- Would you do anything to revise the program?
- Does the program improve my ability to deal with life's challenges to my health?
- Does using the program makes it easier to live a healthier life?
- Is the program useful in my life?
- How satisfied are you with the program?
- Was participating in the program difficult for you?
- Would you recommend the program to people you know?

This dimension will be assessed through surveys and focus groups/interviews with the subjects.

MAINTENANCE **Organizational and Individual Level**

- What was the attrition rate; were drop-outs representative of the target population?
